4.2.1.2 Training of Clinicians

Study personnel will do a demonstration in the use of the decision aid during in-person visits with participating clinics. Training session proceedings will be documented using discretionary video photographing, recording, or note-taking. Clinicians will complete a brief survey after trainings to describe promoting and inhibiting factors to the normalization of the anticoagulation decision aid in clinical practice. Similarly, transcripts and notes from trainings will undergo qualitative analysis to identify promoting and inhibiting factors to the implementation of the shared decision making tool in the clinical sites. Study personnel may also do a reminder of how to use the decision aid as needed (including just-in-time training) or in response to deviations in the quality of delivery observed on video/audio recordings. Brief video clips and storyboards that demonstrate the basic use of decision aids are publicly available at [REDACTED] for clinicians to review at their convenience.

4.2.2 Eligibility Criteria for Patients

Each criterion must be addressed and documented in the patient's case report form for eligibility assessment by the study coordinator. No waivers or exemptions to any eligibility criteria will be permitted.

Inclusion Criteria:

1. ≥ 18 years of age
2. Nonvalvular AF deemed at high risk of thromboembolic strokes (CHA₂D₂-VASc Score ≥ 1 in men, or 2 in women).
3. Able to read and understand (despite cognitive, sensorial, hearing or language challenges) the informed consent document as determined by the study coordinator during consent.

Exclusion Criterion

1. Clinician indicates that patient is not a candidate for a discussion about anticoagulation medication.
2. Cognitive impairments
3. Mechanical values
4. Left appendage occlusion devices (example: Watchman)
- 5.

4.2.3 Identification of Subjects

Participants for all aims will be patients, their caregivers when pertinent, and clinicians. Participation is completely voluntary and we have procedures in place, sanctioned by the Mayo Clinic Institutional Review Board, Hennepin County Medical Center Institutional Review Board (HCMC), Park Nicollet Health Partners Institutional Review Board, UAB Medicine - The University of Alabama at Birmingham Institutional Review Board and University of Mississippi Medical Center Institutional Review Board to ensure that participants have the opportunity to opt out at any time and will not be further approached for participation or to provide data.

At the Mayo Clinic site, upcoming appointment lists for Atrial Fibrillation (AF) patients in primary care, cardiology, neurology, thrombophilia and anticoagulation clinics ECG result lists, medical records and clinician referrals will be reviewed for patient eligibility. Eligible patients will be approached and recruited in person, in a private location (i.e., clinic/exam room) prior to their appointment. Consent will occur by a trained research member as long as needed and until all questions by the subject have been answered. All study activities will occur within scheduled appointments, avoiding the need for additional research visits.

The patient and caregivers (if present), will be asked to provide consent to the recording (video/audio or audio only) of the clinical encounter. If the patient chooses to decline the recording they are still eligible to participate in the study. The study coordinator will quickly setup and start recording before leaving the room. The participants can stop this

recording (video, aimed at the desk, or audio when the video camera is aimed at the ceiling) at any time (the device has a large red start/stop button and an on/off indicator light).

The consent process will include the patient signing authorization to release protected health information forms to allow study personnel to obtain pharmacy prescription records and medical records from outside clinics. If a patient declines to sign an authorization form, he/she will still be eligible for the study but will be excluded from the analysis where information about medication and/or other medical records use is necessary (i.e. adherence analysis). The research team will contact the pharmacies and outside clinics for follow-up, so the patient will not be burdened with additional measures. There will be no monetary or other sort of reimbursement for participants.

4.3 Registration and Randomization of Patients

Prior to registering patients to the study, all of the eligibility criteria on the eligibility checklist will have been met.

Patients will be randomized by the study coordinator after completion of standard informed consent for participation in clinical research including permission to use protected health information.

Registration/randomization is available via REDCap

 this is a secure, web-based application that is HIPPA compliant. Registration/randomization is available 24 hours a day via the REDCap website. Site staff will be provided a login and password by the study statistician.

Prior to accessing the REDCap website, site staff should verify the following:

- All eligibility criteria have been met.
- Informed consent has been obtained.
- Site staff has access to REDCap.

4.4 Intervention

In the intervention group, clinicians will conduct the encounter per standard care procedures with the addition of having access to the Anticoagulation Choice tool. The tool will be accessed online or through an available link in the Electronic Medical Record (EMR). Patient information to complete the calculators of risk (CHA₂DS₂-VASc) and bleeding (HAS-BLED; if needed) are: history of hypertension, congestive heart failure, stroke, vascular disease, diabetes mellitus, renal disease, liver disease, prior or predisposition to bleeding, unstable and/or high INR, whether the patient takes a medication predisposing him or her to bleeding, and the number of alcoholic drinks per week will be entered by the clinician into the tool or will be uploaded from the patients EMR to the tool and a personalized risk will be calculated (**Table 1**). CHA₂DS₂-VASc score of 0: recommend no antithrombotic therapy. CHA₂DS₂-VASc score of 1: recommend antithrombotic therapy with oral anticoagulation or antiplatelet therapy but preferably oral anticoagulation. CHA₂DS₂-VASc score ≥ 2 : recommend oral anticoagulation.² A HAS-BLED score of ≥ 3 indicates that caution is warranted when prescribing oral anticoagulation and regular review is recommended.² Patients can request to receive a printed copy of the tool from their clinician which they can use later to share their decision with others, and to review, confirm or revisit their decision.

Table 1. Assessment of Stroke (CHA₂DS₂-VASc)¹⁴ and Bleeding Risk (HAS-BLED)¹⁵ in Atrial Fibrillation Patients

CHA ₂ DS ₂ -VASc	Score	HAS-BLED	Score
Congestive heart failure	1	Hypertension (SBP >160 mm Hg)	1
Hypertension	1	Abnormal renal and liver function ^b	1 or 2
Age ≥ 75 y	2	Stroke	1
Diabetes mellitus	1	Bleeding tendency/predisposition ^c	1
Stroke/TIA/TE	2	Labile INRs (if on warfarin) ^d	1
Vascular disease ^a	1	Elderly (e.g., age >65 y)	1
Aged 65 to 74 y	1	Drugs or alcohol (1 point each) ^e	1 or 2
Sex category (i.e., female sex)	1		

Maximum score	9	Maximum score	9
---------------	---	---------------	---

Acronym def.: TIA indicates transient ischemic attack; TE, thromboembolic; and INR, international normalized ratio.

- a- Prior myocardial infarction (MI), peripheral artery disease (PAD), or aortic plaque.
- b- Abnormal renal function is classified as the presence of chronic dialysis, renal transplantation, or serum creatinine ≥ 200 mmol/L. Abnormal liver function is defined as chronic hepatic disease (eg, cirrhosis) or biochemical evidence of significant hepatic derangement (bilirubin 2 to 3 times the upper limit of normal, in association with aspartate aminotransferase/alanine aminotransferase/alkaline phosphatase 3 times the upper limit normal, etc). 1 point for each.
- c- History of bleeding or predisposition (anemia).
- d- Labile INR (ie, time in therapeutic range <60%).
- e- Concomitant antiplatelets or nonsteroidal anti-inflammatory drugs, or excess alcohol.

4.5 Standard Care

The clinician will conduct the encounter per their standard of care. As access to the tool will be available to ensure contamination does not occur the study coordinator will inform the clinician prior to entering the room that the patient is to receive standard care and that the tool is not to be accessed.

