1.0 Aims

The goal of this study is to determine the extent to which standard care plus the Anticoagulation Choice tool promotes shared decision making (SDM) and impacts anticoagulation uptake and adherence versus standard care without this tool in patients with nonvalvular atrial fibrillation (AF).

Aim 1. To what extent does use of the ANTICOAGULATION CHOICE tool promote high-quality SDM versus standard care?

Using encounter video recordings and post-visit patient and clinician questionnaires, we will assess **SDM quality** (primary endpoint) **and processes**.

We hypothesize that use of the tool will improve SDM irrespective of patient literacy/numeracy, stroke risk, anticoagulation use at baseline, or type of clinic.

Aim 2. To describe the impact Anticoagulation Choice tool has on the rate of anticoagulation, the choice of anticoagulant, and adherence to anticoagulation in at-risk patients with AF versus the impact of standard care.

Using medical records and pharmacy profiles, we will determine the choice of anticoagulation, changes in anticoagulant use over time, and 12-month drug persistence, in all patients and in subgroups defined by patient literacy/numeracy, stroke risk, anticoagulation use at baseline, and type of clinic. As safety outcomes, we will monitor serious bleeding or strokes requiring medical attention.

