4.0 Research Design & Methods

We will conduct a multicenter randomized trial at the patient level comparing the Anticoagulation Choice tool and standard care versus standard care alone where enrolled clinicians will administer the intervention among patients with nonvalvular AF deemed at high risk of thromboembolic strokes. The study will assess the impact of the interventions on SDM quality and impact on anticoagulation use as well as monitoring safety concerns of strokes and bleeds. Also, as part of this trial, clinician training sessions will be evaluated to describe the normalization process of anticoagulation decision aid in the clinical sites. Data collection will include medical record review, survey completion, and note taking or video/audio recording of the clinical encounter and training sessions.

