4.7.2 SDM processes

To assess SDM processes the recordings of the clinical encounter will be evaluated (video/audio or audio only recordings).

Extent of SDM that took place during the encounter will be assessing the degree of involvement of patients by the clinician in SDM using the OPTIONS scale.⁵³ The scale consists of 12 items scored from 0, no effort to 4, exemplary effort. The 12 items are summed and converted to a 100 point scale. A sample of 20% of the recordings will be assessed by two or more reviewers. Agreement will be assessed by Lin's concordance index⁵⁴, where any value over 0.8 will be considered concordant. If concordance does not occur within the first 20%, the two reviewers will assess cases of difference and review an additional 10 cases to test for agreement. Recordings scored by both reviewers will be averaged.

Impact of SDM on Encounter will be assessed by comparing the length in minutes of the discussion about anticoagulation and of the office visit, when available. Study coordinators when possible will time the encounters in intervention and control visits, prioritizing those encounters in which recording was not allowed. Potential issues preventing assessment of time may be recruitment of another patient.

Fidelity of SDM Tool by the clinician will be assessed by a review of the recording looking for key items to be addressed. A checklist of key elements will be assessed in both arms to assess not only the fidelity but potential contamination. A sum of the components in the checklist will be calculated for each recording and compared between arms. To score the recording first a sample of 20% of the video's will be assessed by two reviewers. Agreement will be assessed by Lin's concordance index⁵⁴, where any value over 0.8 will be considered concordant. If concordance does not occur within the first 20%, the two reviewers will assess cases of difference and review an additional 10 cases to test for agreement. Recordings scored by both reviewers will be averaged. For encounters where

audio and video recording has been declined, a real-time assessment will occur at the consent of the clinician and the patient. The study coordinator will conduct these real-time reviews.

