4.7.3 Anticoagulation Use

Rate of anticoagulation: The key indicator of the choice to start an anticoagulant will be its prescription in the EMR prescription module (observed discussions and patient/clinician accounts may not reflect decisions confirmed after the visit with a prescription, for example, after the clinician or the patient checked other information or with other informants). After this primary ‘decided as prescribed’ approach, we will conduct secondary analyses using patient/clinician reported and video-observed decisions. Decisions may be for starting or not an anticoagulant in the start cohort. It is possible that there may be some decisions to stop anticoagulation in the review cohort, but we expect start and review cohorts to contribute information about choice of anticoagulant.

Choice of anticoagulant: We will review the EMR and 10-month pharmacy profiles (to stand for the 12-month profile given the automatic expiration of pharmacy records at 1 year) to determine the prescribed anticoagulant and whether and when switches to another agent or to no anticoagulant took place.

Together, they should capture choice and switches even when these occur as a result of changes in clinician (e.g., from cardiology to primary care). When available, we will note the documented reasons from clinical notes for choosing and switching as well as with which clinician the change was made (e.g primary, cardiology, etc.).

Anticoagulation persistence: Patients will identify the pharmacy(-ies) they use to fill their prescriptions and authorize us to obtain their prescription drug fill data. We will calculate anticoagulation persistence, using the percent days covered (PDC) based on prescription refill behaviors (total days supply of anticoagulant filled / total days of observation from the first prescription fill date; range 0-100%). We will also pull all pharmacy refills for the 12 months prior to enrollment. This will allow us to calculate persistence for prior use of anticoagulants for the review cohort to compare to persistence post encounter and see if there is an impact.

Warfarin use: For patients who choose to stay on warfarin, we will also use as secondary measures of adherence: (a) the proportion of INR tests obtained/scheduled; and (b) percentage of time at therapeutic target (typically INR 2-3).

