6.3 Potential Risks

Potential risks to patient subjects should be minimal. Given that the intervention has been extensively pilot tested and no adverse outcomes occurred, we do not expect early termination due to harm. The intervention is an educational tool for use during the clinic visit to help patients make decisions about anticoagulation medications. The tool does not make recommendations or result in prescriptions without the participation of the clinician, and the tool is not to be used outside a clinical visit in which a clinician can place the information in context.

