6.4 Protection and Confidentiality

6.4.1 Subject privacy

In this study, the privacy of all study participants will be protected by avoiding the use of names on all research data (including field notes, transcribed conference call, meeting tapes, audio-and video-recordings of the interviews, transcripts). All study participants will be identified by a unique study code number only. The link between the code number and study participant's identity will be stored within the remote data capture system. Medical records will be abstracted electronically using computers that are not linked to any Mayo mainframe computer. Names of those who decline participation in the study will be maintained in a do-not-contact list, so they will not be contacted multiple times (as patients are likely to have multiple appointments at participating clinics during the study). All research material outside of what is stored within the remote data capture system will be maintained on a secure server at the KER Unit at Mayo Clinic and locked in file cabinets.

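### The bar on tool use for standard-care patients, and the contamination check, stop at the index visit, while Aim 2 compares switching and persistence for 10 to 12 months

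*Combined protocol and SAP*

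**What the plan says.** Randomization is by patient (section 4.0), and enrolled clinicians are trained on the tool before their first enrolled patient (4.2.1.1), so a trained clinician can see patients of both arms. The tool is reached online or by an EMR link (4.4), and no restriction of access by arm is described.

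For the control arm, section 4.5 recognises the contamination risk and relies on a notice at the encounter: "the study coordinator will inform the clinician prior to entering the room that the patient is to receive standard care", and that the tool must stay closed. Nothing is said about later visits. Section 6.3 adds that "the tool is not to be used outside a clinical visit in which a clinician can place the information in context", which does not exclude a control patient's later clinical visit.

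Contamination is checked in section 4.7.2: "A checklist of key elements will be assessed in both arms to assess not only the fidelity but potential contamination". The checklist is scored on the recording of the encounter or, where recording is declined, by real-time review of it.

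Aim 2 runs much longer: "Using medical records and pharmacy profiles, we will determine the choice of anticoagulation, changes in anticoagulant use over time, and 12-month drug persistence" (1.0). Records are abstracted to 12 months (4.6), and pharmacy fills are requested to 10 months (calendar of events). Section 4.7.3 expects these sources to "capture choice and switches even when these occur as a result of changes in clinician", and plans to note documented reasons for a choice or switch, and with which clinician it was made. The items in the calendar at 12 months are bleeds, strokes, INR tests, prescriptions, pharmacy fills and a phone contact where needed. Later use of the tool is not among them.

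**The concern.** The comparator in section 1.0 is standard care in which the tool is absent. That condition is enforced and checked on one day, whereas the switching and persistence outcomes build up over the following 10 to 12 months. A control patient who returns to a trained clinician, or is passed to another one, could be shown the tool without breaking any rule in the protocol. The monthly review of protocol adherence (6.1) would have no deviation to find.

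If that happens and the tool has an effect, part of the effect moves into the control arm and the arms look more alike. A null result on persistence could then mean either that the tool does not change persistence or that controls also received it, and the planned data could not separate the two.

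**Working it through.** **Time windows, side by side**

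| Item | Period covered | Section |
|---|---|---|
| Bar on tool use in controls | Index encounter | 4.5 |
| Contamination checklist | Index encounter | 4.7.2 |
| Aim 1 primary endpoint (SDM quality) | Index encounter and post-visit survey | 1.0, 4.6, 4.7.1 |
| Start decision (EMR prescription) | Mainly the index decision | 4.7.3 |
| Switches and persistence | To 10 months (pharmacy) and 12 months (record) | 4.6, 4.7.3 |
| Tool use after the index visit | Not collected | 4.6, calendar |

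Only the switching and persistence row runs well past the bar and the check.

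**Is a return visit to a trained clinician plausible?** Section 4.7.4 treats the absence of recent utilization before month 12 as a case needing direct contact. Section 4.7.3 gives a move from cardiology to primary care as an example, and at the Mayo site both are recruitment sources (4.2.3). So it is plausible. None of these sections says how often it happens or that the tool would be used.

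**The plan's own power figure (4.9.2).** Inputs: 999 participants, 90% starting or continuing, 85% of records obtained, 60% versus 69%, two-sided alpha 0.05, stated power 80%. I assume 1:1 allocation (no ratio is stated), read 60% and 69% as proportions of patients, and make no allowance for clustering.

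- Records: 999 × 0.90 × 0.85 = 764, which agrees with the plan's figure of about 765. Per arm: 765 / 2 = 382.5.
- Standard error under no difference: √(2 × 0.645 × 0.355 / 382.5) = 0.0346.
- Standard error under the alternative: √((0.60 × 0.40 + 0.69 × 0.31) / 382.5) = 0.0344.
- Power = Φ((0.09 − 1.96 × 0.0346) / 0.0344) = Φ(0.644) = 74.0%.

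The stated 80% does not reproduce; it would need 886 records. Using 999 × 0.90 = 899 records gives 80.6%, so the loss of records may have been left out. That is a separate error, and 74.0% is the correct base for what follows.

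**Illustration of dilution.** Let c be the full-effect equivalent share of controls exposed later, that is, the share exposed times the fraction of the effect they gain. The tool arm stays at 69%. The control rate becomes 0.60 + 0.09c and the difference 0.09 × (1 − c).

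| c | Control rate | Difference | Power |
|---|---|---|---|
| 0 | 60.0% | 9.0 points | 74.0% |
| 5% | 60.45% | 8.55 points | 69.7% |
| 10% | 60.9% | 8.1 points | 65.1% |

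The documents give no value of c; these are assumptions. Persistence is measured as percent days covered from the first fill, so a control first exposed at month 3 of a 10-month profile has already accrued 3 of the 10 months unexposed. If 10% were exposed and gained half the effect, c would be 0.10 × 0.5 = 5%.

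**The case against.** The best case for the plan is that the intervention is access to the tool in one encounter, analysed by intention to treat. The effect of offering it then, followed by whatever care comes next, is a legitimate pragmatic contrast, and the analysis is valid for it. This stands. What remains is that the plan does not state this reading, and section 1.0 describes a comparator without the tool.

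It can also be said that the index clinician, once told the allocation, may carry it forward. That may help with that clinician, but not with others.

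A reader might infer more than the documents support:

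- **That later exposure of controls is expected.** Section 6.4.1 does say "as patients are likely to have multiple appointments at participating clinics during the study", but it is explaining a do-not-contact list for people who declined. It is not about enrolled controls or anticoagulation discussions. Nor does the remark on changes in clinician in 4.7.3 show that the next clinician is trained.
- **That the trial's main result is compromised.** SDM quality is measured at or just after the index visit, and the start decision belongs mainly to that visit.
- **That nothing could reveal late use.** The documented reasons for switching in 4.7.3 might show some instances, though not use that leads to no switch.
- **That contamination accounts for the gap below the stated 80% power.** The drop from 80% to 74.0% has nothing to do with it.

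Aim 2 is also worded as descriptive. That lowers the weight of the power figures, but a description still needs a comparator whose exposure is known, and section 4.9.2 does power persistence as a two-sided test.

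**Conclusion.** The point holds for the switching and persistence outcomes of Aim 2. Both the bar and the check end with the index encounter, and later tool use is not a planned data item. Any dilution is conditional on two things the documents do not establish: that controls are shown the tool later, and that it then acts in the same direction as at the index visit. Its size is unknown. Under the stated assumptions, a full-effect equivalent of 5% or 10% of controls costs 0.45 or 0.9 points of the 9-point difference and about 4 or 9 points of power from 74.0%; later or partial exposure costs less. Because 74.0% is already below the stated 80%, there is no spare power to absorb it. This is an inexpensive improvement in how Aim 2 can be interpreted. It does not challenge the primary endpoint or the validity of the intention-to-treat comparison.

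**What to change.** 1. Amend section 4.5 so that the coordinator's instruction to enrolled clinicians says that the tool is not to be accessed with that standard-care patient until the 12-month follow-up ends.
2. Add one field to the 12-month abstraction already planned, in both arms, for documented tool use after the index visit. Report it by arm, with the caution that a blank does not prove that the tool was not used.
3. Keep intention to treat as the analysis, and state in section 4.9.1 that Aim 2 estimates the effect of offering the tool at the index visit.

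The cost is protocol wording, one abstraction field and a small burden on clinicians and abstractors; no extra patients or visits are needed. The main weakness is that later use will be incompletely documented. The instruction also reaches only the clinicians who receive it. An EMR flag at each site or an exposure-adjusted sensitivity analysis could be considered, but both are open to debate and the point does not depend on them.
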